2. SUMMARY OF PROPOSALS

2.1 ABSTRACT:

The detection of malarial retinopathy (MR) in cerebral malaria (CM) patients currently requires expensive equipment and extensive training. We have developed a computerized software-based analysis of retinal images obtained by handheld fundus cameras that is >90% specific. The purpose of this study is to evaluate the performance of a software in detecting malarial retinopathy in retinal images obtained using hand-held fundus cameras by non-ophthalmologist clinicians. The overall aim of the proposed study is to collect digital retinal image data of clinically diagnosed CM patients and utilize the images to develop and test the performance of software algorithms (ASPIRE) for detecting specific signs of MR and for detecting the presence of MR. The performance of the software will be measured against the binocular indirect ophthalmoscopy (BIO) examination (if available) performed by an ophthalmologist for determining the presence of MR (reference standard) and/or against the grading of established retinal graders. Participants between the age of 6 months and 12 years who present with coma, a positive malaria test, and clinical diagnosis of CM, will be enrolled at the time of admission at the respective participating hospital(s). The imager will be masked to MR detection results. The retinal images will be graded by an ophthalmologist for the detection of specific signs of MR. The retinal images will be used to develop and test algorithms for detecting specific MR lesions and overall MR presence. The sensitivity and specificity of the software algorithms against grader's image grading will be determined to evaluate the performance of each algorithm and its usability in identifying MR. This study would be a first step in the validation of retinal image analysis software for assessment of MR. The results of the

study will be used to inform initiatives to spread the use of software-based detection of MR to preclinical settings in which CM patients are seen. Results will also be useful in planning the studies to quantify the detection of MR lesions and analyze large datasets in objective manner.

LAY SUMMARY OF RESEARCH PROTOCOL

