3.5 SPECIFIC OBJECTIVES

The primary objectives are:

1. To collect mydriatic retinal images of at least N= 50 pediatric subjects clinically diagnosed with CM at each of the study sites located in Nigeria, Africa. Retinal images will be collected from the participating clinics/hospitals by clinicians over a period of 2 years. The activity has been piloted and found to be within the scope of clinicians in Nigeria.
2. To determine the sensitivity and specificity of software algorithms for classifying clinically diagnosed CM patient into MR positive or MR negative using the images obtained with up to three retinal cameras, compared with retinal graders' grading (in all cases) and the clinical reference standard (BIO) when possible.

Secondary objectives are:

1. To determine the positive predictive value (PPV) and negative predictive value (NPV) of software algorithms for classifying clinically diagnosed CM patient into MR positive

or MR negative using the images obtained with up to three retinal cameras, compared with retinal graders' grading (in all cases) and the clinical reference standard (BIO) when possible.

2. LITERATURE REVIEW:

Cerebral malaria (CM) is a fatal neurological syndrome of malarial disease. The *World Malaria Report 2019* estimates that malaria claimed 381,000 lives in Africa in 2018, over 65% of whom were children under five years of age [iv]. CM is one of the largest contributors to pediatric malarial deaths, and approximately 23% of children are found to be misdiagnosed with CM, which leads to incorrect treatment and results in mortality or neurological disability in thousands of children in Africa [v,vi,vii,viii,ix]. There is a significant market need for low-cost and easy-to-use technology to improve CM diagnosis and save lives.

Malarial Retinopathy (MR) manifests as a series of retinal lesions highly specific (>95%) to CM and therefore can be used to improve the diagnostic accuracy of CM. VisionQuest proposes the development and clinical deployment of an artificial intelligence (AI) system, Auto Detection Software for Plasmodium Infection in Retinal Exams (ASPIRE), that offers the first AI-supported MR detection software integrated with a low-cost and portable retinal camera, a system that can be operated by minimally trained personnel such as medical technician or nurse without the need of an ophthalmic specialist.

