3. METHODOLOGY

STUDY SITE

This study will be conducted within the malaria endemic regions of Nigeria. The study population will be enrolled at each of the following study sites located within the malaria endemic region of Nigeria;

1. University College Hospital, Ibadan
2. Amino Kano University, Kano
3. General Sani Abacha Specialist Hospital, Damaturu
4. State Specialist Hospital, Sokoto
5. Massey's Children Hospital, Lagos Island

STUDY DESIGN^[1-5]

This will be a prospective, pivotal, multi-center clinical study.

STUDY POPULATIONS

Study participants involved in this study will be children aged between 6 months and 12-year-old who have been diagnosed with cerebral malaria.

Inclusion Criteria:

- Children aged 6 months- 12 years admitted to any one of the study sites who satisfy the standard clinical case definition of cerebral malaria

- Blantyre coma score of ≤ 2
- Known results of a positive malaria test (blood smear or malaria rapid diagnostic test)
- Consent provided by parents/caregivers of the eligible children.

Exclusion criteria:

- Children admitted who satisfy the standard clinical case definition of cerebral malaria, but when there is no clinician/nurse available to do an examination within 6 hours of admission.

SAMPLING^[1-3]

Sample size determination

We aim to demonstrate MR detection performance on a validation dataset collected with continuous enrollment of clinically diagnosed CM patients with or without malarial retinopathy. About 61% of CM-diagnosed patients show a manifestation of CM in retina, in form of retinal lesions, called malarial retinopathy (MR) [xi,xii,xiii]. Rest 39% of CM-diagnosed patients do not exhibit MR. So, the prevalence of MR in CM-diagnosed patients is 61%.

The study hypothesis is that the sensitivity and specificity of detecting MR using ASPIRE's MR detection algorithm is non-inferior to the clinical reference standard, which is defined as the reading of retinal images for MR detection by ophthalmic specialists such as ophthalmologists.

Non-Inferiority test design:

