According to literature studies, the sensitivity and specificity of ophthalmologists in reading retinal images to detect retinal diseases are 89% and 87%, respectively [xiv]. We aim to demonstrate that the sensitivity and specificity of our software-based test are non-inferior to the ophthalmologist's standard, with 7% non-inferiority margin [xv]. Therefore, the lower-bound on both sensitivity and specificity will be at least equal or greater than the minimum sensitivity and specificity requirements for a diagnostic software as recommended by the FDA, of 80% and 80%, respectively.

The study will use a non-inferiority design and seek to demonstrate that the experimental method (software-based reading of retinal images) is not appreciably worse than the standard method (ophthalmologist's reading of retinal images). The reason behind using a non-inferiority design is that the proposed software-based test is not expected to be better than the standard test (ophthalmologist's reading of retinal images) on a primary efficacy end point in clinical study; but the availability, accessibility, affordability, and compliance of the proposed software-based test will be better outside the clinical study and hence efficacy will be better outside the study. Therefore, the proposed software-based test has potential to provide greater clinical benefit and/or outcome at the cost of being non-inferior in performance compared to the standard test [xvi].

In this study design, we used Blackwelder formula [xvii,xviii] to calculate sample size:

$$N_{cases} = \frac{(Z_\alpha + Z_\beta)^2}{(\pi_S - \pi_E - d)^2} \left[\pi_E(1 - \pi_E) + \frac{\pi_S(1 - \pi_S)}{\lambda} \right],$$

where

$$\lambda = \left(\frac{1 - Prev}{Prev} \right).$$

The conjectured accuracy (sensitivity/specificity) of the standard test is π_s , the conjectured accuracy (sensitivity/specificity) of the proposed diagnostic/experimental test is π_E . $Z\alpha$ and $Z\beta$ are standard values assuming 80% power and 5% Type-I error. "Prev" is prevalence of disease-positive patients, and "d" is a non-inferiority margin.

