To establish that our software-based test is non-inferior to the standard test (ophthalmologist’s reading of images), with sensitivity of 0.89 and specificity of 0.87; we will require a minimum number of disease-positive (MR-positive) “cases” of 366, and minimum number of disease-negative (MR-negative) “controls” of 234. In total, we will require a minimum sample size of 600 CM-diagnosed patients to validate our proposed test.

Once we enroll the minimum number of MR-positive and MR-negative patients required, we propose to validate the software-based test performance on the collected sample and verify if the resulting sensitivity/specificity is within the margin of difference. Upon verification, it can be concluded that the experimental test is non-inferior to the standard test within a non-inferiority margin of 7%.

Sampling procedure [11]

The procedure will be as follows:

1. Pupillary light response is checked and then pupils are dilated with 0.5% tropicamide and 10% phenylephrine, repeated after 10 minutes.
2. Ophthalmologist, clinician or nurse takes iNview photos (at least 8 photos: 4 optic disc center, 4 macula center)
3. Ophthalmologist, clinician or nurse takes VistaView photos (at least 8 photos: 4 optic disc center, 4 macula center)
4. Ophthalmologist, clinician or nurse takes Pictor-Plus photos (at least 8 photos: 4 optic disc center, 4 macula center)
5. The retinal photos captured by Pictor-Plus, VistaView, and iNview cameras may be transmitted to a laptop computer or smartphone automatically and analyzed instantaneously for image quality by a computer-based software. The software will either accept or reject each photo based on high or low image quality, respectively. A graphical display on a laptop computer or smartphone

will be shown to the imager (ophthalmologist, clinician, or nurse) that demonstrates the captured image and whether it was accepted or rejected.

6. The retinal photos captured by Pictor-Plus, VistaView, and iNview cameras will be analyzed instantaneously for detection of malarial retinopathy (MR) by a computer-based software. The imager (ophthalmologist, clinician, or nurse) will be masked to MR detection results due to non-interventional nature of this study.
7. The analysis of retinal photos for image quality and MR detection will be fully automatic and handled by a laptop computer or smartphone and will not require manual inputs or interference from the imager.
8. Ophthalmologist performs BIO when possible.

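### The all-patient analysis measures agreement with image grading, so it cannot show non-inferiority to the ophthalmologist's reading, and the 0.82/0.80 limits are not on that scale

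*Combined protocol and SAP*

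**What the plan says.** **The claim.** Sample size determination (3. Methodology) states the hypothesis as non-inferiority to "the clinical reference standard, which is defined as the reading of retinal images for MR detection by ophthalmic specialists". Non-Inferiority test design takes the comparator's accuracy from the literature: "the sensitivity and specificity of ophthalmologists in reading retinal images to detect retinal diseases are 89% and 87%, respectively". It sets a 7% margin and adds that "the lower-bound on both sensitivity and specificity will be at least equal or greater than the minimum sensitivity and specificity requirements" of 80% and 80%. The Conclusion of the sample size section says the investigators will "verify if the resulting sensitivity/specificity is within the margin of difference", after which "it can be concluded that the experimental test is non-inferior to the standard test within a non-inferiority margin of 7" per cent.

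**The analysis.** Section 3.5, primary objective 2, compares the software with the retinal graders' "grading (in all cases) and the clinical reference standard (BIO) when possible". Section 2.1 says "The retinal images will be graded by an ophthalmologist for the detection of specific signs of MR". Data analysis, study question #2, plans sensitivity and specificity with 95% CIs. Its visible text describes neither a software-minus-reader difference nor a test against the margin.

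**Who grades.** Section 2.1 also speaks of performance "against the grading of established retinal graders". Section 3.4 names a certified grader, and the camera examination procedure names one independent grader. Type of data to be collected mentions one independent grader and, elsewhere, graders. No text assigns two readings to each image.

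**What the reference is called.** Sample size determination calls image reading the clinical reference standard. Section 3.5 gives that name to BIO.

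**The concern.** Non-inferiority to a reader needs three things: the software, the reader, and a standard against which both are scored. In the all-patient analysis only the first two exist, and the reader serves as the standard. The reader's own accuracy is then not observed, and the difference that the 7-point margin refers to cannot be estimated.

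What remains is a one-sample check of the software against fixed limits, 0.89 - 0.07 = 0.82 and 0.87 - 0.07 = 0.80. Those limits come from readers scored against some other standard. Agreement with an imperfect grader is a different quantity: it depends on the grader's errors and on how far software and grader err on the same patients. Good software can fail and borderline software can pass. Study design calls the study pivotal, so its headline conclusion should be one that its data can test.

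**Working it through.** **1. The plan's own figure.** Inputs from Non-Inferiority test design: margin 0.07, power 80%, Type I error 5% (sidedness not stated), prevalence 61%. λ = 0.39/0.61 = 0.639, and one-sided 5% gives (1.645 + 0.842)² = 6.18.
- Specificity: (6.18/0.0049) × 0.87 × 0.13 × (1 + 1/0.639) = 365.9, so 366 cases. 365.9 × 0.639 = 233.9, so 234 controls. The total of 600 is reproduced.
- Sensitivity: 316.7 and 202.5, so 317 and 203 (318 and 203 printed).

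The arithmetic is sound. But the formula contains a variance term for the standard test, so it presumes an observed comparator that the all-patient design lacks.

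**2. The scale.** A reading scored against itself has sensitivity and specificity 1.00. Seven points below that is 0.93, not 0.82 or 0.80.

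**3. Model for agreement.** Assume the grader is truly 0.89/0.87.
- P(grader positive) = 0.61 × 0.89 + 0.39 × 0.13 = 0.5936, so of 600 patients about 356 are grader-positive and 244 grader-negative.
- Within each true class, the probability that software and grader are both right is p_S·p_G + ρ√[p_S(1-p_S)p_G(1-p_G)]. The probability that both are wrong has the same ρ term. ρ is the error correlation, which the documents do not give.
- Apparent sensitivity = [0.61·P(both positive | MR) + 0.39·P(both positive | no MR)]/0.5936. Apparent specificity is the analogue over 0.4064.
- Perfect software needs no ρ: 0.61 × 0.89/0.5936 = 0.915 and 0.39 × 0.87/0.4064 = 0.835.

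**4. Probability of passing both limits.** The assumed rule is that both exact one-sided 5% lower bounds exceed 0.82 and 0.80, which needs at least 305/356 and 206/244. The two probabilities are multiplied, because the patient groups are separate.

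| True software accuracy | ρ | Apparent sens/spec | Passes both |
|---|---|---|---|
| Perfect | none needed | 0.915/0.835 | 39% |
| 0.89/0.87 (equal to grader) | 0 | 0.825/0.745 | <0.1% |
| | 0.25 | 0.869/0.808 | 7% |
| | 0.37 | 0.890/0.839 | 44% |
| | 0.5 | 0.913/0.872 | 92% |
| | 1 | 1.00/1.00 | 100% |
| 0.82/0.80 (at the limits) | 0 | 0.767/0.698 | <0.1% |
| | 0.25 | 0.820/0.775 | <0.1% |
| | 0.37 | 0.846/0.812 | 3% |
| | 0.5 | 0.873/0.852 | 57% |
| | 0.6 | 0.894/0.883 | 96% |
| | 0.75 (about the largest feasible) | 0.926/0.930 | about 100% |

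A valid 5% test would pass software at the limits at most 5% of the time. Letting the grader-positive count vary changes little (perfect software 37%; at the limits with ρ = 0.5, 56%).

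**5. Other grader accuracy.** If the grader is placed at the corners of the pilot range in 3.1 Background (sensitivity 87%-100%, specificity 75%-87%), perfect software appears at 0.845 to 0.923 for sensitivity and 0.787 to 1.00 for specificity. Its joint pass probability runs from 0.5% to 100%.

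**6. As a fixed goal only.** If agreement with the grader is itself 0.89/0.87, then 366 and 234 patients give 0.984 × 0.880 = 87% joint power against 0.82/0.80.

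**7. BIO subset.** Take BIO as truth, a true difference of zero, a paired comparison, a 7-point margin and 80% power at one-sided 5%: n = 6.18 × 2p(1-p)(1-ρ)/0.0049.
- Specificity (p = 0.87): about 285, 214 or 143 MR-negative patients at ρ = 0, 0.25 or 0.5. Dividing the unrounded values by 0.39 gives about 732, 549 or 366 BIO patients.
- Sensitivity (p = 0.89): about 247, 185 or 124 MR-positive patients. Dividing by 0.61 gives about 405, 304 or 203.
- With 100 BIO patients (39 MR-negative), power for specificity is 23%, 28% or 37%.

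**The case against.** **A second reading may exist.** The list of comparisons under study question #2 is missing from the text as extracted, and several sections say graders in the plural. An ophthalmologist's reading scored against a separate grader is conceivable. This stands as a caution and is why the first request is to say who reads each image. But no available text assigns a second reading, and literature accuracy minus 7 points would still be off the agreement scale.

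**It is really a fixed goal.** The test design section names an 80%/80% floor, and a fixed goal against grading is a legitimate design with reasonable power (step 6). That is right, but meeting it shows agreement with grading, while the Conclusion claims non-inferiority to the standard test. The 0.82 limit is derived rather than printed.

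**The pass rates depend on a rule that the plan does not state.** This also stands. The check is worded loosely and no level is given for the lower bound. On point estimates alone, perfect software passes 92% of the time. With the lower limit of a 95% CI it passes 26%. For software at the limits with ρ = 0.37, 3% becomes 62% or 1%. Under each of these rules the result still turns on the grader's errors and how far they are shared.

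**The inputs are assumed.** The range of ρ has no source in the documents. The pilot figures were measured against BIO, which 3.1 Background says is not a true gold standard, and the worst corner pairs two extremes not reported together. The figures therefore show that the rule is uncalibrated in both directions; they do not estimate the actual bias.

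**Conclusion.** The concern holds and must be fixed before analysis. The hypothesis and Conclusion commit to non-inferiority to the ophthalmologist's image reading, while objective 2 makes that kind of reading the reference in all patients. On the available text, the all-patient data cannot test the claim, and more patients would not change that.

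The sizes are illustrations under the stated model and rule. With the grader at the plan's own 0.89/0.87, perfect software passes 39% of the time. Software equal to the grader passes between <0.1% and 100%, depending on ρ. Software at the limits passes up to about 100%. The logical conflict does not depend on these figures. Confidence is high on the conflict and lower on the BIO part, because the lost list may already include BIO comparisons.

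**What to change.** 1. Name masked specialist image grading as the primary reference for all patients. State who grades and how many readings each image gets, reconciling 2.1, 3.4 and the camera examination procedure. Give the term clinical reference standard one meaning.
2. In Sample size determination, Non-Inferiority test design and the Conclusion, replace non-inferiority to the ophthalmologist with sensitivity and specificity against specialist grading, with 95% CIs and a statement that grader error remains in the figures.
3. If a pass/fail goal is kept, present it as a goal for agreement with the grader. Justify it on that scale before the analysis, state the decision rule, and give the agreement at which its power holds.
4. In patients with BIO, as a secondary analysis, score software and grader both against BIO. Report paired differences with 95% CIs and the number with BIO. Note that BIO is imperfect and that these patients are selected by its availability. Keep any software-versus-reader statement for this analysis, and call it descriptive unless the number is adequate (step 7). If BIO comparisons are already listed, keep them and add the paired difference.

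**Cost.** Protocol wording and at most one extra analysis of data already collected. Estimation needs no extra patients: with 600, the 95% half-widths near 0.89/0.87 are 1.96√(0.89 × 0.11/356) = 0.033 and 1.96√(0.87 × 0.13/244) = 0.042. If 0.82/0.80 stays as a goal, 600 may be too few: software equal to the grader passes 44% of the time at ρ = 0.37 and 7% at 0.25. The claim becomes narrower, grader error stays in the primary result, and the BIO comparison may remain descriptive.

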A statistical calculator developed by the National Institutes of Health - National Cancer Institute (NIH-NCI) Statistics group [xix] (that implements Blackwelder's formula) was used to perform the sample size calculations. To verify the calculations, an "R-Studio" package was used that includes a function to calculate the sample size needed for two sample non-inferiority test. The R package is "epiR" and the function that performs sample size calculations is "epi.ssninfb()" [xx]. The documentation for this function also references the Blackwelder (1982) method used by the NIH-NCI Statistics group, and contains two examples illustrating how the function is used to perform sample size calculations for a non-inferiority study with a binary outcome measure.

Input parameters:

The input parameters required for sample size calculation are the expected response rates in each group (experimental and standard), non-inferiority margin, power, alpha, and prevalence of disease-positive (MR-positive) patients.

For our study, we propose to determine a sample size required to test our software-based test for MR detection for binary classification (“MR detected” or “MR not detected”). The conjectured sensitivity of the standard test is $\pi_s = 0.89$ (ophthalmologist’s sensitivity), and the conjectured sensitivity of the proposed experimental test is $\pi_E = 0.89$. At the noninferiority margin of $d = 0.07$, how many subjects should we include in the study to maintain 80% power and 5% Type-I error, while assuming the prevalence of Referral (MR-positive or MR detected) in the CM-diagnosed population to be 61%?

Results

The input parameters used to demonstrate the conjectured sensitivity of the experimental test of 0.89, yielded the sample size requirement as the minimum number of disease-positive “cases” of 318, and minimum number of disease-negative “controls” of 203. Using the same method, the input parameters used to demonstrate the conjectured specificity of the experimental test of 0.87, yielded the sample size requirement as the minimum number of disease-positive “cases” of 366, and minimum number of disease-negative “controls” of 234.

Conclusion

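### The 80% power belongs to sensitivity and specificity taken one at a time; the plan gives no power for its conclusion, which needs both to be non-inferior

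*Combined protocol and SAP*

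**What the plan says.** All of this is in the Methodology chapter of the combined protocol and SAP, mostly under Sample size determination.

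- **The claim is joint.** The hypothesis opens "The study hypothesis is that the sensitivity and specificity of detecting MR" and treats the two measures as one claim of non-inferiority. Under Non-Inferiority test design the aim is to show that "the sensitivity and specificity of our software-based test are non-inferior", and the text adds that "the lower-bound on both sensitivity and specificity will be at least equal or greater than" a stated minimum of 80% for each. The Conclusion sizes the study to establish non-inferiority "with sensitivity of 0.89 and specificity of 0.87".
- **The power is per measure.** The formula uses "standard values assuming 80% power and 5% Type-I error". Under Input parameters, the sensitivity question asks how many subjects are needed to "maintain 80% power and 5% Type-I error". The Results then give 318 cases and 203 controls for sensitivity. A second, separate calculation follows: "Using the same method, the input parameters used to demonstrate the conjectured specificity of the experimental test of 0.87" lead to 366 cases and 234 controls.
- **The larger pair is adopted.** The Conclusion takes 366 + 234 = 600 as the minimum for the combined claim.
- **What is not stated.** Joint power is not mentioned. Sidedness is not given. The Data Analysis section promises sensitivity and specificity with 95% confidence intervals but names no non-inferiority test and no decision rule.

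**The concern.** When a claim succeeds only if two tests both succeed, its power cannot exceed the smaller of the two separate powers and is usually below it. Taking the larger of two sample sizes guarantees at least 80% for each test. It does not guarantee 80% for passing both.

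The plan calls the study pivotal. A reader of the Conclusion would take the risk of missing the stated goal, with software that performs exactly as conjectured, to be one in five. The plan contains no calculation of that risk. It also states no allowance for ungradable images or missing data, so any fall below 366 and 234 would reduce whatever power there is.

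**Working it through.** **Inputs (all from Sample size determination).** Conjectured sensitivity 0.89 and specificity 0.87, the same for software and ophthalmologist; margin d = 0.07; power 80%; type I error 5%; MR prevalence 0.61, so λ = 0.39/0.61 = 0.639.

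**1. Reproduce the plan's sample sizes.** With equal rates p in both groups, the printed formula is

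cases = (z_α + z_β)² / d² × p(1 − p)(1 + 1/λ), controls = λ × cases.

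At one-sided 5%, z_α = 1.645 and z_β = 0.842.

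| Measure | p(1 − p) | Cases, one-sided 5% | Controls, one-sided 5% | Plan | Two-sided 5% |
|---|---|---|---|---|---|
| Sensitivity | 0.0979 | 316.7 | 202.5 | 318 / 203 | 403 / 258 |
| Specificity | 0.1131 | 365.9 | 233.9 | 366 / 234 | 465 / 297 |

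The plan's figures therefore come from a one-sided 5% level (sensitivity cases differ by one). A two-sided level does not reproduce them.

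**2. Power of each test at the adopted 366/234, same formula.**

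power = Φ( 0.07 / √[p(1 − p)(1/366 + 1/234)] − 1.645 ), with 1/366 + 1/234 = 0.007006.

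- Sensitivity: SE = √(0.0979 × 0.007006) = 0.02619; 0.07/0.02619 = 2.673; Φ(1.028) = 84.8%.
- Specificity: SE = √(0.1131 × 0.007006) = 0.02815; 0.07/0.02815 = 2.487; Φ(0.842) = 80.0%.

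**3. Joint power under the printed formula.**

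- If the tests are independent: 0.848 × 0.800 = 0.678, about 68%.
- With no assumption on dependence: at least 0.848 + 0.800 − 1 = 0.648, at most 0.800.
- With z = 1.960, as a two-sided 95% interval would imply: 0.762 × 0.701 = 0.534, about 53% under independence.

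The upper bound of 80% is reached only if every dataset that passes on specificity also passes on sensitivity.

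**4. Joint power under tests that fit the data.** Sensitivity is estimated in MR-positives only and specificity in MR-negatives only. These are different children, so multiplying the two powers is justified here. The fixed goals are 0.89 − 0.07 = 0.82 and 0.87 − 0.07 = 0.80.

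| Exact one-sample tests | Sensitivity, n = 366 | Specificity, n = 234 | Joint |
|---|---|---|---|
| One-sided 5% | at least 313 correct; power 98.4% | at least 198 correct; power 88.0% | 86.6% |
| Two-sided 95% interval (one-sided 2.5%) | at least 315 correct; power 96.6% | at least 200 correct; power 78.9% | 76.2% |

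If the software and an ophthalmologist are instead compared on the same children, the power at one-sided 5% is Φ(0.07/√[2p(1 − p)(1 − r)/n] − 1.645), where r is the within-patient correlation of the two readings. The plan gives no value for r, so these are assumptions:

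- r = 0: 0.916 × 0.728 = 67%
- r = 0.2: 0.959 × 0.808 = 78%
- r = 0.4: 0.988 × 0.896 = 89%

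**The case against.** The best defence is that the plan makes no arithmetic error and may have enough patients. Its sample sizes reproduce, the 80% is attached to the individual calculations, and no sentence claims 80% joint power. With exact one-sample tests at the plan's own 5% level, taken one-sided, joint power at 600 is about 87%, so there is no shortfall.

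Most of this stands, and it limits the point. A reader might infer that the trial has 68% power and will fail one time in three, or that 600 is too few. The documents do not support either inference, for two reasons. First, the 68% mixes two premises. Each separate power puts both patient groups into each test, while the multiplication treats the two tests as resting on separate groups. Taken literally, the formula uses the same 600 children twice, and only the 65% to 80% range is secure. Second, the actual test is not specified, and plausible choices run from 53% to 89%.

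The defence does not remove the gap itself. The Conclusion treats 600 as sufficient for both measures together, and the only power figure behind it is per measure. The slash between sensitivity and specificity in the Conclusion is loose wording. The hypothesis and the aim join the two, and the lower-bound sentence refers to both.

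The lay summary mentions 800 patients. If all 800 were used for validation at 61% prevalence (488/312), the printed formula would give 0.925 × 0.890 = 82%. Those patients are from Nigeria and Malawi and serve development as well as testing, and the Conclusion sets the validation minimum at 600.

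**Conclusion.** The point holds: the stated 80% is not the power of the conclusion the study intends to draw, and no joint power is given. On the plan's own formula at one-sided 5%, joint power at 366/234 is about 68% under independence, and it cannot exceed 80% under any dependence.

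How far the true power is from 80%, and in which direction, cannot be settled from the documents, because the test and its sidedness are not fixed. One-sample exact tests give about 87% at one-sided 5% and about 76% on a two-sided 95% interval.

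All these figures assume that the software's true accuracy equals the conjectured 0.89 and 0.87, and that the full 366 and 234 children have usable images and a reference grading.

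**What to change.** In Sample size determination:

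1. State that success requires non-inferiority on both sensitivity and specificity.
2. Name the test for each measure and its sidedness, and make the decision rule agree with the 95% intervals in Data Analysis.
3. Replace the 80% with the joint power under that test. One-sample exact tests of 0.89 against 0.82 (n = 366) and 0.87 against 0.80 (n = 234) would be reported as about 87% at one-sided 5%, or about 76% if the two-sided 95% interval decides.
4. If the printed formula is kept, report about 68% and label it as conditional on that formula and on independence. This is the weaker option, since the formula does not match how the two measures are estimated.

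The cost is a few sentences and one restated figure, with no extra patients. The downside is that the restated power may be less favourable than 80%. Patients would have to be added only if the sponsor keeps the printed formula and wants 80% joint power under independence: about 760 in total (464 MR-positive and 296 MR-negative; 0.914 × 0.876 = 0.80).
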